8.3.3.3 ECG Processing and Quality Check

Safety ECGs and Holter data received by the ECGs Core Laboratory will be translated to a readable and analyzable ECG format, according the ECGs Core Laboratory procedure.

The ECGs Core Laboratory will ensure that all Site ECGs Manual requirements have been followed. In the event that a problem with Safety ECGs or Holter data is identified (e.g.: inappropriate length, inconsistency of with the ECGs protocol, inappropriate demographic identifier, poor quality data), the investigational site will be notified concerning the nature of the problems and the steps required for corrective action. The ECGs Core Laboratory will follow-up on all cases requiring remedial action by the investigational sites. Guerbet (or the ECGs Core Laboratory) may conduct site training for the investigator site in case of recurring data quality issues.

8.3.3.4 Expert ECG Reader(s) Training

ECGs Core Laboratory will train expert off-site readers to the trial ECG reading specifications.

 CONFIDENTIAL	Protocol No. GDX-44-006 Version No. 5.0 including amendment 03 Date 31 August 2018	Page 51 / 80
----------------------------------------------------------------------------------------------------------	------------------------------------------------------------------------------------------	--------------

8.3.3.5 Blinded Assessment of ECGs

ECGs from Holter recorder database including all evaluable ECGs will be assessed by one or more expert reader(s), with expertise in the interpretation of ECGs for QT and arrhythmia assessment, who will not participate in the trial, and does not have affiliation with the institution where the trial will be conducted. The reading will be performed in a strictly fully blinded manner.

ECGs Core laboratory has to ensure that all ECGs (except safety ECGs) of a given patient have to be read on the same day by the same reader and the reader has to be blind about subject, product, date and time-point identifier [2]

8.3.3.6 Inter and Intra-Reader Variability Assessment

The assessments of inter and intra-reader variability will be done by the ECGs Core Laboratory and according their internal quality system.

8.3.3.7 ECG Warehouse and Final Deliverables

Guerbet (or its ECGs Core Laboratory) will submit all ECGs extracted from Holter data to the required competent authority's warehouse as requested format.

Safety ECGs, all Holter data and original ECGs copies extracted from Holter data will be maintained in a secure environment. The ECGs Core Laboratory will maintain a centralized ECGs archive that will contain every data received from the clinical investigators for the trial and original ECGs copies extracted from Holter. Measurements will also be stored so that these data may be audited if necessary. The resulting database will be transferred to Guerbet after database lock for archiving.

8.4 Other Centralized Trial Procedures

8.4.1 P03277 plasma concentration and long term elimination samples

Details on samples handling for plasma concentration and long term elimination assessment, will be provided to the investigational site in a separate document.

Blood samples

A peripheral catheter will be placed until the 8 hour timepoint for blood collection in the forearm (controlateral to the injection site).

For the collection at 24h, 1 and 3 months after the last IMP/AMP administration, blood samples will be collected by direct venipuncture.

For P03277 analysis, blood will be collected into requested tubes. Plasma will be obtained after blood collection by centrifugation and aliquots stored at -20°C [-18 to -36°] for analysis. Plasma will be divided into two different aliquots P03277 analysis.

In case of remaining blood collected, it will be discarded.

One aliquot for P03277 determination will be sent on frozen condition to the analytical center. One aliquot collected will be kept in the clinical center for the trial duration and will be sent to the analytical center only if necessary. At the end of the trial as described in [section 3.2](#), non-sent aliquots will be discarded.

Urine samples

Urine fraction will be collected at 1 and 3 months after the last IMP administration.

 CONFIDENTIAL	Protocol No. GDX-44-006 Version No. 5.0 including amendment 03 Date 31 August 2018	Page 52 / 80
---------------------------------------------------------------------------------------------------	------------------------------------------------------------------------------------------	--------------

One aliquot will be sent to the analytical center. One aliquot collected will be kept in the clinical center and will be sent on frozen condition to the analytical center only if necessary. Aliquots will be placed into polypropylene tubes, will be tightly capped and stored at -20°C [-18 to -36°] until shipment for analysis. After having aliquoted the samples, the remaining urine will be destroyed.

8.4.2 Sample management

The samples will be stored at -20°C [-18 to -36°] before being sent in frozen condition to the qualified analytical center in order to be kept frozen during the shipment.

The schedule of the sample shipments to the analytical center will be discussed with the sponsor during the trial. A few days before the shipment, a fax or email will be sent to the analytical center with at least the following information:

- Date and time of shipment,
- Name and address of the carrier.

The exact content of the shipment should be sent to the analytical center.

The determination of P03277 in plasma and urine will be performed using a validated LC-MS/MS method.

Specific analytical protocols will be established for analysis of P03277. Data will be reported in a separate report. All analytical methods used in this trial will be validated prior to any sample analysis.

9 SAFETY REPORTING

The Investigator will report to the sponsor any adverse event whether related or not to the investigational medicinal product, serious or not, that occurred during the confinement period of a trial subject and only IMP or moxifloxacin related adverse events or AESI (related or not) during follow-up period. Special situations such as treatment errors, suspicion of transmission of an infectious agent via an IMP or moxifloxacin, unusual failure in efficacy, overdose (symptomatic or not), misused, drug exposure during pregnancy or breastfeeding even if uneventful, suspected drug-drug interaction with another product (symptomatic or not) will also be reported to the sponsor.

The definition, modalities of collection and reporting are provided below.

9.1 Adverse Event

9.1.1 Definition of Adverse Event

An Adverse Event (AE) is any untoward medical occurrence in a patient or clinical investigation subject administered a pharmaceutical product and which does not necessarily have to have a causal relationship with this treatment.

An adverse event (AE) can therefore be any unfavourable and unintended sign (including an abnormal laboratory finding, for example), symptom, or disease temporally associated with the use of a medicinal product, whether or not considered related to the medicinal product (ICH E2A).

9.1.2 Collection and Recording of Adverse Events

The Investigator or his/her designee will invite the subject to report any experienced abnormality as part of the usual clinical follow-up. In addition, any biological value assessed as significant by the Investigator should be considered as AE.

In order to ensure complete safety data collection, all Adverse Events occurring from the screening visit (ICF signature) until the end of the confinement period, must be reported and followed even if no IMP or moxifloxacin were administered. Only related Adverse Events (serious or not) or AESI (related or not) will be recorded during follow-up visits.

AE should be reported and documented in the medical file and the appropriate section of the CRF

As reminder the subject's participation is defined as the period from the screening visit (ICF signature) to the last trial visit in the general case and defined in [section 10](#) in case of premature discontinuation.

Reported AE is followed up from onset to recovery or stabilization of sequelae. If no follow-up is performed, the investigator must provide a justification in the medical file.

9.1.3 Description of Adverse Events

The following guidelines and definitions should be used by the investigator for the description of an AE when reporting information in CRF and any specific AE report forms:

- **Nature of AE:** preferably an overall diagnosis or syndrome, rather than individual symptoms or signs. The investigator must report AE using standard medical terminology. The same terms should be used in the source documentation and in the CRF.
- **Date and time of onset:** date and clock time of the AE start
- **Intensity:**

- Mild: the subject is aware of the sign or symptom, but it does not interfere with her/his usual daily activities and/or it is of no clinical consequence
- Moderate: the AE interferes with the usual daily activities of the subject or it is of some clinical consequence
- Severe: the subject is unable to work normally or to carry out his/her usual daily activities, and/or AE is of definite clinical consequence.
- **Date of the event end** (or consolidation): The real date of event end will be entered if the event has come to its end. If the AE is still ongoing by the time of end of trial follow-up for the subject (i.e. last trial visit), the subject should be followed-up until AE resolution or a justification should be provided by the Investigator (i.e. chronic disease) in the medical file.
- **Causal relationship to the Investigational Medicinal Product or moxifloxacin:**
 - Related: the definition of adverse reaction implies a reasonable possibility of a causal relationship between the event and the IMP or moxifloxacin. This means that there are facts (evidence) or arguments to suggest a causal relationship.
 - Not related: Applicable when no IMP or moxifloxacin have been administered (pre-administration period) or when no causal relationship exists between the trial drug and the event, but an obvious alternative cause exists (e.g. the subject's underlying medical condition or concomitant therapy).
- **Causal relationship to a trial procedure:**
 - Related
 - Not related
- **Outcome:**
 - Recovered/Resolved: the AE is no longer present at any intensity or return to baseline values for biological data.
 - Recovered/Resolved with sequelae: the AE is resolved but residual effects are still present.
 - Not recovered/Not Resolved: the AE is still present at the last contact with the subject.
 - Fatal: this AE caused or directly contributed to subject's death.
- **Action taken with regard to administration of the IMP or moxifloxacin:**
 - No Action: for AE occurring during the pre-administration/procedure or post-administration/procedure period, or if the IMP or moxifloxacin administration remained the same in spite of AE being present.
 - IMP or moxifloxacin withdrawn.
- **Other action taken:**
 - IMP unblinding
 - AE-targeted medication: the subject took a medication (either prescription or non-prescription) specifically for this AE. The drug(s) should be reported in the appropriate section of the CRF ("concomitant drug" section)
 - Other AE-targeted action: therapeutic measures other than corrective drug administration (e.g. ice, heating pad, brace, cast...) or subject underwent a procedure (surgery, physiotherapy, additional laboratory test...) for this AE. The therapeutic measure(s) should be reported in the appropriate section of the CRF ("Action other than drug administered for the AE" section)
- **Assessment of the seriousness of the AE:** see [Section 9.2](#) for SAE definition.

9.2 Serious Adverse Event

9.2.1 Definition of Serious Adverse Event

A Serious Adverse Event (SAE) is any untoward medical occurrence that at any dose (ICH E2A):

- Results in death

- Is life-threatening
- Requires inpatient hospitalization or prolongation of existing hospitalization
- Results in persistent or significant disability /incapacity
- Is a congenital anomaly / birth defect
- **Is an important medical event**

Medical and scientific judgement should be exercised in deciding whether expedited reporting is appropriate in other situations, such as **important medical events** that may not be immediately life-threatening or result in death or hospitalization but may jeopardize the patient or may require intervention to prevent one of the other outcomes listed in the definition above. *These should also usually be considered serious.*

Examples of such events are intensive treatment in an emergency room or at home for allergic bronchospasm; blood dyscrasias or convulsions that do not result in hospitalization; or development of drug dependency or drug abuse.

Note: Life-threatening in the definition of a serious adverse event refers to an event in which the subject was at risk of death at the time of the event; it does not refer to an event which hypothetically might have caused death if it were more severe.

In case of a SAE, the investigator is responsible for the measures to be taken to ensure the safety of the trial participants.

Severe / Serious: the term “severe” is used to describe the intensity (severity) of a specific event (within the scale mild, moderate, severe). This is not the same as “serious”, which is based on subject/event outcome or action criteria. The event itself may be severe but of relatively minor medical significance.

In this protocol, the following situations will not be considered as SAE, providing that they are clearly documented as such in the subject’s source data:

- Any hospitalization that had been planned before the trial and that will take place during the trial, provided there is no aggravation of the disease to which it is related.
- Hospitalizations, which are not associated to an adverse event (such as hospitalization for checkup).

9.2.2 Reporting Serious Adverse Events (SAE)

All SAEs occurring from ICF signature until end of confinement period of each subject **must be reported immediately** by the investigator to the sponsor. Only SAE related to IMP, moxifloxacin or procedure must be reported during the follow-up period. The investigator must immediately forward to Guerbet Pharmacovigilance department a duly completed SAE report form  provided by Guerbet with trial documents, even if it is obvious that more data will be needed in order to draw any conclusion:

- **By Fax #: [name]**
- **Or by e-mail to: [contact]**

In case of emergency, Guerbet Pharmacovigilance department may be contacted at: **[name].**

SAEs, as for all adverse events, have to be reported also in medical file and in the appropriate section of the CRF (see section 9.1.2)

In order to allow the assessment and eventual subsequent regulatory reporting of the case, the following minimum information should be filled in:

- Subject's details including age, sex and subject's trial enrollment number
- Subject's medical history relevant to the assessment of the event
- Type of event by reporting a diagnosis or if not available, symptoms
- Date and time to onset of the event
- End date of the event (will be reported in a follow-up report if the event is still ongoing at the time of first notification)
- Date and time of investigational drug or moxifloxacin administration,
- Causal relationship to the investigational drug, moxifloxacin or procedure (mandatory)
- Outcome at the time of reporting

If the investigator is aware of any new relevant information concerning an SAE (e.g.: outcome or any information that can have an impact on the assessment of the seriousness or the causal relationship between the SAE and the IMP or moxifloxacin), he has to send it immediately to Guerbet Pharmacovigilance department on a SAE report form [REDACTED] as a follow-up report.

The initial and follow up reports shall identify the trial subject by his/her Identification Number assigned for the purpose of the trial.

Additional information (e.g. autopsy results, biological values ...) or clarifications may be required by the Sponsor in a timely fashion to ensure accurate follow-up and assessment of each case and should be transmitted, anonymized, with a specific form [REDACTED] as soon as they are available.

SAEs should be followed up by the investigators until complete recovery of the subject or, if not possible, until stabilization of sequelae. The investigator may be requested by Guerbet to provide follow-up information in order to comply with current regulations as well as for comprehensive assessment purposes.

SAEs associated with trial procedures are to be notified using the same reporting procedure as described above.

In addition, if occurring after the end of the subject's follow-up period defined for this trial, serious adverse and/or unexpected events, that the Investigator thinks may be associated with the trial medication/procedure must be reported to the sponsor regardless of the time between the event and the end of the trial.

According to local requirements, Guerbet or its representatives will communicate relevant safety information to the appropriate agency (ies), IEC and/or all active investigators, as it becomes available.

The transmission of the information to the sponsor does not release the investigator from his responsibility to inform the regulatory authorities, if applicable.

9.3 Special situations

9.3.1 Cases of overdose, lack of efficacy, drug-drug interaction, medication errors or misuses

The safety information regarding the following special situations has to be collected and reported by the investigator with the same procedure as for AE, even if uneventful:

- Unintentional treatment errors (e.g.: wrong route of administration),
- Misuse: where the medicinal product is intentionally and inappropriately used not in accordance with the protocol,
- Occupational exposure to an IMP/AMP
- Suspected drug-drug interaction with another product.
- Overdose: In this protocol, the overdose is defined as more than 0.3 mmol/kg for P03277 and more than 400mg for moxifloxacin. Any overdose, with or without adverse event, will be reported as AE and, in addition, on SAE form if the associated event is serious.

If one of these situations leads to an AE or SAE, the safety information will be managed as for AE or SAE accordingly and will follow the appropriate reporting procedure.

9.3.2 Pregnancy

Any participating subject who becomes pregnant or is aware of a pregnancy (subject's partner) during trial participation should inform immediately the investigational site. The female subject should be immediately withdrawn from IMP or moxifloxacin administration.

Any pregnancy (with or without an Adverse Event) of women participating in the trial or of partners of men participating in the trial, that is discovered after the ICF signature until Day 17, i.e. 7 days after the last IMP/AMP administration, must be reported to Guerbet Pharmacovigilance *via* the SAE Report Form  (see section 9.2.2).

Pregnancy will be monitored until delivery (health of infant up to 8 weeks of age) or early termination.

Specific forms "history and start of pregnancy" and "course and outcome of pregnancy" will be provided to the investigational sites. These forms will be used to collect information on the medical history of the pregnant woman and any risk factor of pregnancy complication, and on the follow-up and outcome of the pregnancy.

Any complication of pregnancy will be reported as an AE or SAE, as appropriate.

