 - (4) Blood sampling for biology assessment: Hematology: Red Blood Cells (RBCs), White Blood Cells (WBCs), neutrophils, eosinophils, basophils, lymphocytes and monocytes, platelet count, hemoglobin, hematocrit, Mean red blood Cells Volume (MCV). Biochemistry: sodium, potassium, magnesium, chloride, glucose, urea, creatinine, eGFR, total protein, calcium, total protein, phosphorus, total bilirubin, unconjugated and conjugated bilirubin, Aspartate Amino Transferase (AST), Alanine Amino Transferase (ALT), alkaline phosphatase, Lactate DeHydrogenase (LDH). Triglycerides (TG).
 - (5) For screening blood and urine sampling and serology, results have to be available at the latest at D 1
 - (6) Only for female subject of childbearing potential or with amenorrhea for less than 12 months
 - (7) P03277 plasma concentration sample will be drawn at pre-dose up to 24 hours post dose : [-1hour, 5min, 10 min, 20 min, 30min, 1 hour, 1.5 hours, 2 hours, 3 hours, 4 hours, 8 hours, 24 hours] (5, 10 and 20 min are not applicable for AMP period).
 - (8) 25 hours ongoing from one hour before trial products administration up to 24 hours post-dose
 - (9) Unless for moxifloxacin which will be administered per os and on open label
 - (10) Adverse events will be recorded from screening visit to end of confinement except pregnancy (subject's or subject's partner) that will be recorded up to Day 17. During follow-up period, only related AE and AESI will be recorded.
 - (11) IMP volume to be injected at Day 1 should be based on weight measured at inclusion visit or the day before (Day -1)
- Time windows allowance have been defined for each procedures as described in the relevant study plans listed in section 18.2

TRIAL DIAGRAM

(example of possible sequences)

[figure not shown]
PC= Positive Control, P= Placebo, CD= P03277 at anticipated clinical dose, SD= P03277 at supra-clinical dose.

Screening can be done within 28 up to 1 days before inclusion.

Minimum trial duration for subjects: 95 days

[figure not shown]
Maximum trial duration for subjects: 122 days (In case of ICF is signed 28 days before inclusion).

SIGNATURE PAGE

PRINCIPLE INVESTIGATOR STATEMENT

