3.2 Trial Duration

The duration of subject’s participation could be from 95 days up to 122 days (in case the subject signs the informed consent form (ICF) within 28 days before inclusion).

Within 4-weeks up to 1 day run-in period, subjects will be screened for the trial. Inclusion in the trial will occur the day the subject will be admitted to the phase I clinical trial unit for the first administration period of the allocated sequence (subjects may be admitted in the phase I clinical trial unit at Day -1 to

ensure availability of all results prior to administration). Each subject will have 4 administration periods. Period's duration for moxifloxacin, placebo period, P03277 at clinical dose and P03277 at supra-clinical dose periods will each be 72 hours. The total duration for all periods will be 12 days.

During the 12 days of assessment and monitoring, the subject will have to stay in the phase I clinical trial unit. Healthy volunteers will be discharged on Day 12 after that all trial procedures have been performed and that all safety results have been reviewed by the investigator who will determine that it is safe to discharge the subject.

One month and 3 months following the last IMP/AMP administration on Day 10, subjects will be asked to come back at the phase I clinical trial unit to assess the P03277 long term elimination (in plasma and urine).

For each subject, all ECG parameters will be extracted from the 12-lead Holter ECG in triplicates (3 ECGs taken in close succession according to the ECG core lab specifications) and read centrally by an ECG core lab. The mean of the triplicate ECGs recordings will be considered for each timepoint.

P03277 plasma and urine concentration samples will be analyzed and data reported by an analytical center as described in [section 8.4](#). All other drawn samples will be kept by the analytical center for the trial duration and then will be discarded.

The trial will be considered as completed once all the ECG collected for all the subjects are reviewed by a core lab and all P03277 plasma concentration and elimination data are available.

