8.1.3.5 Days following administration

- Day 2, Day 5, Day 7 and Day 11, T[24 hours]:
 - Vital Signs (systolic and diastolic Blood Pressure in supine position after 10 minutes of rest, Pulse Rate).
 - Blood samples collection for P03277 plasma concentration assessment (always after vital signs) as close as possible of defined time point. Real time collection have to be entered in the subject's record and appropriate form

In addition, the following information have to be entered in the subject's record and appropriate form:

- Meal start and end time during the Holter recording
- Holter end date and time information

Tolerance at injection site (except for AMP): burning, pain, eruption, extravasation, inflammation, or other. In case of injection-site pain, the subject will be asked to specify the level of pain using a visual analogic scale (VAS, XXXXXXXXXX) from 0 (no pain) to 10 (maximal pain).

- Day 3, Day 6, Day 9:
 - Body weight
 - Blood sample collection for biological safety assessment.

8.1.4 (Day 12) - Discharge

On Day 12, the healthy subjects will be discharged after that all trial procedures had been performed and after an appropriate clinical examination including:

- Physical examination
- Body weight
- Vital signs
- 12 lead ECG
- Blood sample collection for biological safety assessment

and based on which investigator has determined that it is safe to discharge the subject.

In case of abnormal findings, the subject will be asked to stay at the clinical unit for appropriate follow-up.

8.1.5 (Day 38) and (Day 94) – Follow-up Period

Healthy subjects will be asked to come back in the phase I clinical trial unit at Day10 + 1 month and Day10 + 3 months.

- The Investigator will question on any possible GBCAs injection since the discharge day (name of contrast agent injected and tolerance will be recorded);
- Only AEs related to the IMP or moxifloxacin, whether serious or not and AESI should be reported and documented in the medical file and the appropriate section of the CRF.
- Blood samples and urine collection for long term P03277 elimination assessments.

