8.1.6 Confinement period

The healthy subjects will be confined in the phase I clinical unit from Day 1 to Day 12 (2 day post last dosing) in order to perform investigational procedure and safety follow-up.

During the confinement period, no grapefruit (and grapefruit derivated products), alcohol, tobacco and beverages with xanthine bases (tea, coffee, chocolate) will be permitted for healthy subjects. Correct hydration of the subjects should be ensured during the confinement period. The clinical staff will ensure that subjects drink at least 1.5 liters of water per day. The healthy subjects will be discharged on Day 12. All subjects will be asked to come back to perform safety follow-up visits on Day 10+ 1 month and on Day 10 + 3 months.

 CONFIDENTIAL	Protocol No. GDX-44-006 Version No. 5.0 including amendment 03 Date 31 August 2018	Page 49 / 80
---------------------------------------------------------------------------------------------------	------------------------------------------------------------------------------------------	--------------

If newly-emergent changes in safety profile occur, further examination can be performed for as long as necessary, to assure that the changes have resolved, and/or that the subject is stable.

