### 2.3. Other safety criteria

#### 2.3.1. Clinical and biological safety

##### 2.3.1.1 Adverse events

Adverse events will be recorded throughout the start of subject participation up to the end of confinement period except pregnancy (subject's or subject's partner) that will be recorded up to day 17 (7 days after the last IMP/AMP administration). During follow-up period only related AEs and AESI will be recorded.

CONFIDENTIAL	STATISTICAL ANALYSIS PLAN N° GDX-44-006 VERSION N° 2.0      DATED: 24JUL2018	██████████ Page 10 / 57
--------------	---	----------------------------

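### Protocol 9.3.2 limits mandatory pregnancy reporting to pregnancies discovered by Day 17, which conflicts with Section 9 and with a participation period that runs to Day 94

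*Protocol*

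**What the plan says.** **The limit.** Under Protocol 9.3.2 a pregnancy in a participating woman or in a male participant's partner "that is discovered after the ICF signature until Day 17, i.e. 7 days after the last IMP/AMP administration, must be reported" on the SAE form. A reported pregnancy is then followed to delivery or early termination, and the infant's health to eight weeks. Footnote 10 of the flow chart repeats the limit for adverse event recording: "except pregnancy (subject's or subject's partner) that will be recorded up to Day 17". The synopsis, Protocol 7.2.2.1 and SAP 2.3.1.1 carry the same day.

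**Passages without the limit.** The opening of Protocol Section 9 lists special situations to be reported to the sponsor, among them "drug exposure during pregnancy or breastfeeding even if uneventful", and gives no closing day. The first sentence of 9.3.2 asks subjects to tell the site at once of a pregnancy at any time during participation, and 9.1.2 states that "the subject's participation is defined as the period from the screening visit (ICF signature) to the last trial visit". The last trial visit is Day 94.

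**The schedule.** "The healthy subjects will be confined in the phase I clinical unit from Day 1 to Day 12" (8.1.6). The flow chart and 8.1.2 show one pregnancy test, on urine at inclusion, for women of childbearing potential or with amenorrhea of less than 12 months. For Day 38 and Day 94, section 8.1.5 says: "Only AEs related to the IMP or moxifloxacin, whether serious or not and AESI should be reported". Pregnancy is not on the AESI list in 9.3.3, and neither visit includes a pregnancy question.

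**The concern.** A reporting window for pregnancy has to allow for the delay between conception and discovery. The window in 9.3.2 closes by date of discovery, one week after the last possible dose, and nothing scheduled after inclusion would bring a pregnancy to light before then.

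A woman who tells the site at the Day 38 visit that she was already pregnant when dosed has done what 9.3.2 asks of her. Section 9 then tells the site to report the exposure, while the reporting sentence of 9.3.2 does not require it. If the site treats 9.3.2 as the operative rule, the SAE form and the follow-up of mother and infant are not triggered. She may have received both P03277 doses and moxifloxacin. A count of pregnancies collected this way would be hard to interpret, because zero could mean either none occurred or none was found in time.

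**Working it through.** **Inputs from the documents**
- Last administration: Day 10 (Protocol 3.2: "One month and 3 months following the last IMP/AMP administration on Day 10").
- Reporting limit: Day 17 (9.3.2).
- Confinement: Day 1 to Day 12 (8.1.6).
- Follow-up visits: Day 38 and Day 94, each with a 3-day window either side (flow chart).
- Only pregnancy test: inclusion visit, Day -1 or Day 1.

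**Inputs that are assumptions.** The documents give no time from conception to a positive test or to discovery. I take 10 to 14 days to a positive urine test and 10 to 28 days to discovery.

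**The plan's own figures.** 10 + 7 = 17, as stated. 10 + 28 = 38 and 10 + 84 = 94, matching the visit days.

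**Rule.** A pregnancy conceived on day *c* and discovered *L* days later falls inside the 9.3.2 window only if *c* + *L* ≤ 17.

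**Conceptions after discharge (Day 12 to Day 17), including those of male subjects' partners.** The oldest is 17 − 12 = 5 days old when the window closes, so capture needs *L* ≤ 5. At *L* = 10 the earliest discovery is 12 + 10 = Day 22; at *L* = 28 it is 12 + 28 = Day 40. None is inside the window anywhere in the assumed range. At *L* up to 21 all are known by Day 38 (17 + 21 = 38); at *L* = 28 all are known by Day 45, well before Day 94.

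**Conceptions just before dosing that the inclusion test misses.** Take the test on Day 1 and number days consecutively through zero. If a test needs *T* days to turn positive, the missed conception days run from 2 − *T* to 1, which is *T* days. The youngest is 17 − 1 = 16 days old on Day 17. The table shows how many of these conception days are discovered by Day 17.

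| Days to positive test, *T* | *L* up to 16 | *L* = 21 (*c* ≤ −4) | *L* = 28 (*c* ≤ −11) |
|---|---|---|---|
| 10 | 10 of 10 | 5 of 10 | 0 of 10 |
| 12 | 12 of 12 | 7 of 12 | 0 of 12 |
| 14 | 14 of 14 | 9 of 14 | 2 of 14 |

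In every cell, all of these pregnancies would be discovered by Day 38. A test at Day 17 would be expected to find them, but none is scheduled, so *L* here is the time until the woman herself notices.

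**Passages side by side.** For a pregnancy present at dosing and disclosed on Day 38:
- Section 9: report the exposure to the sponsor.
- 9.3.2, first sentence, with 9.1.2: the subject must inform the site.
- 9.3.2, reporting sentence: reporting is mandatory only up to Day 17.
- Synopsis, 7.2.2.1, flow-chart footnote 10 and SAP 2.3.1.1: recording ends at Day 17.

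**The case against.** A reader might infer that pregnancies are reportable only if discovered by Day 17. The protocol as a whole does not say that: Section 9 has no day limit, 9.3.2 does not forbid later reports, and subjects must inform the site until the last visit. This stands, and it makes the problem a conflict between passages rather than a prohibition. It does not remove the problem. Section 9 defers to the detail that follows it; 9.3.1 does not list exposure in pregnancy, and the only specific procedure is in 9.3.2. Section 9 also does not clearly reach a partner's pregnancy or a conception after the last dose.

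A second tempting inference is that the rule captures almost nothing. For pregnancies present at dosing, the table rules that out as a general statement: with discovery within 16 days, all are captured. A third is that the 7 days were meant to cover conceptions on Day 12 to Day 17, so that the rule fails its own purpose. No passage states which pregnancies the window is for, and it could equally be a short period for learning of pregnancies already present.

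Safeguards also count. Entry requires a negative test and approved contraception for women of childbearing potential, although that criterion does not extend to men's partners. A congenital anomaly is an SAE (9.2.1), and related SAEs are reportable during follow-up and afterwards (9.2.2). That covers an adverse outcome judged related, but not a pregnancy without complications.

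**Conclusion.** The point holds as an inconsistency with a practical consequence. The Day 17 discovery limit conflicts with the open-ended duty in Section 9 and with a participation period ending on Day 94.

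Conceptions after discharge cannot realistically be discovered in time; this needs only the assumption that discovery takes more than 5 days. For pregnancies missed by the inclusion test, capture under 9.3.2 runs from all to none over the assumed latencies, and the documents give no figure to narrow that.

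Few cases are expected. The planned 48 subjects comprise 24 women (6 × 4 sequences), not all of childbearing potential, and 24 men whose partners are covered. The primary QTcF analysis, its type I error and the sample size are untouched. This is a modest correction to safety data capture, worth making because it is cheap.

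**What to change.** Reconcile Protocol Section 9, 9.3.2, 7.2.2.1, the synopsis and flow-chart footnote 10 with SAP 2.3.1.1. Define a reportable pregnancy by exposure, or by estimated conception, within the sponsor's existing period (consent signature to Day 17), and make it reportable whenever it is discovered up to the last visit. Add a question about pregnancy, in the subject or a partner, to the Day 38 and Day 94 visits in 8.1.5 and the flow chart, so that the wider definition has a scheduled means of capture.

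No additional test is proposed, and neither the 7-day period nor any dosing or withdrawal rule changes. The cost is an amendment, matching CRF and SAP wording, and one question at each of two existing visits.
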